3.7 Follow-Up Period

For SAEs, the patient must remain under observation until the SAE has subsided or stabilized and all serious findings have returned to normal or stabilized. Any follow-up information to an initial SAE report must be updated in the eCRF. Serious Adverse Events are to be reported if they are known to occur within 30 days following the last study visit.

Appendix C. Excluded Medications and Dosing Modifications

Subjects taking any of the medications listed in Appendix C may participate if they are otherwise eligible AND the medication can be safely held during the following times:

- Immediately before the 1st IP administration (Day 0) until at least 10 hours after the 2nd IP administration (Day 1)
- Immediately before the 3rd IP administration (Day 8) until at least 10 hours after the 4th IP administration (Day 9)

Cardiac:

- Digoxin
- Flecainide
- Amiodarone

Psychiatric:

- Duloxetine (Cymbalta)
- Lithium
- Clozapine (Clozaril)
- Thioridazine (Mellaril or Melleril)

Neurologic:

- Carbamazepine (Tegretol)
- Phenobarbital (Luminal and Solfoton)
- Phenytoin (Dilantin, Phenytoin Sodium, Phenytek)
- Fosphenytoin (Cerebyx)
- Riluzole (Rilutek; Used to treat amyotrophic lateral sclerosis ALS)

Antimicrobial/fungal:

- Aminoglycosides (Eg. amikacin, gentamicin, kanamycin, neomycin, netilmicin, paromomycin, streptomycin, tobramycin)
- Azole antifungals (fluconazole, miconazole, voriconazole) (if absolutely necessary, levels must be subtherapeutic or therapeutic)
- Macrolides (clarithromycin)
- Antivirals (nelfinavir, indinavir, saquinavir)

Oral hypoglycemic/Anti-Diabetes drugs:

- Glimepiride (Amaryl)
- Glyburide (DiaBeta, Glynase PresTab, Micronase)

Anticoagulants/ Antiplatelet:

- Warfarin
- Full dose aspirin

Others:

- Cyclosporine
- Methotrexate
- Nitroglycerin
- St. John's Wort
- Theophylline
- Tyrosine Kinase Inhibitors (list included further down in this appendix)
- Tizanidine (Zanaflex)
- Tacrine

Version 4.0, 18NOV2021

• Diclofenac

Version 4.0, 18NOV2021

Continuation of Excluded Medications

Sensitive Substrates CYP2C9, CYP2C19, CYP1A2, Other (OATP1B1)

	Sensitive substrate	Drugs with a narrow therapeutic
		range
CYP2C9	Glyburide	Fosphenytoin
	Losartan	Phenytoin
		Warfarin
		Glimepiride
		Diclofenac
		Bosentan
CYP2C19		Phenytoin
CYP 1A2	Clozapine	Theophylline
	Olanzapine	Tizanidine
		Warfarin
		Ramelteon
		Tacrine
		Duloxetine
		Mexiletine
		Riluzole
Other	Corticosteroids	
(OATP1B1)	Thyroid hormones	
	Eluxadoline	
	Eltrombopag	
	Pioglitazone (Actos) - monitor blood glucose levels closely or	
	½ dose QD	
	Enzalutamide	
	Colchicine (½ dose QD until 10 hours after the last (2 nd) IP	
	administration	
	Venlafaxine (skip dose on study drug Day 2; then resume as	
	usual)	
	Atorvastatin (QOD or ½ dose QD until 10 hours after the last	
	(2 nd) IP administration; unless willing to modify as directed.) Rosuvastatin (QOD or ½ dose QD until 10 hours after the last	
	(2 nd) IP administration unless willing to modify as directed.)	
	Desipramine (QOD or hold until 10 hours after the last (2 nd) IP	
	administration)	
	Atomoxetine (hold)	
	Repaglidine- monitor blood glucose level closely (CYP2C8)	
	Repugname- momor blood glucose level closely (CYP2C8)	

Tyrosine Kinase Inhibitor List (CYP2C8)

afatinib	crizotinib	imatinib	ponatinib	Tarceva	Xalkori
axitinib	dasatinib	Imbruvica	regorafenib	Tasigna	Zaltrap
Bosulif	erlotinib	Inlyta	sorafenib	Tivopath	ziv-
bosutinib	Gilotrif	lapatinib	Sprycel	tivozanib	aflibercept
cabozantinib	Gleevec	Nexavar	Stivarga	Tykerb	_
Caprelsa	ibrutinib	nilotinib	sunitinib	vandetanib	
Cometriq	Iclusig	pazopanib	Sutent	Votrient

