Fisetin 100 mg capsules or Fisetin (with cellulose) powder (in water, other chilled or room-temperature drinks, apple sauce, pudding, yogurt, or enteral hydration/ nutrition solutions) will be administered orally for 2 consecutive days on study Days 0 and 1. To reduce senescent cell abundance by a "hit-and-run" approach, the full daily doses of Fisetin will be administered within 30 minutes. The investigational supplies will be obtained from Vital Nutrients, a contracted GMP manufacturer. Fisetin capsules supplied by Vital Nutrients are opaque blue in color. Fisetin powder is a green yellow color. We established stability parameters for Fisetin in collaboration with Mayo Clinic's Department of Laboratory Medicine and Pathology. We acquired an IND for Fisetin after establishing botanical sourcing, GMP isolation by Vital Nutrients, assurance of lack of contaminating pesticides, heavy metals, and solvents, and stability, degradation, and accelerated toxicity testing.

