4.2 Patient Selection Criteria

4.2.1 Inclusion Criteria:

All of these criteria must be met:

- Males and females, at least 18 years of age, capable and willing to provide informed consent;
- Patient must have received a diagnosis of COVID-19 infection within the last 10 days;
- Outpatient setting (not currently hospitalized or under immediate consideration for hospitalization);
- Patient must possess at least one of the following high-risk criteria: 70 years or more of age, obesity (BMI ≥30 kg/m²), diabetes mellitus, immune deficient state (primary or secondary immunodeficiency), history of hypertension (systolic blood pressure ≥150 mm Hg), known respiratory disease (including asthma or chronic obstructive pulmonary disease, current or previous smoking), known heart failure, known coronary disease, fever of ≥38.4°C within the last 72 hours, dyspnea at the time of presentation, bicytopenia, pancytopenia, or the combination of high neutrophil count and low lymphocyte count;
- Female patient is either not of childbearing potential, defined as postmenopausal for at least 1 year or surgically sterile, or is of childbearing potential and practicing at least one method of contraception and preferably two complementary forms of contraception including a barrier method (e.g. male or female condoms, spermicides, sponges, foams, jellies, diaphragm, intrauterine device (IUD)) throughout the study and for 30 days after study completion;
- Patient must be able and willing to comply with the requirements of this study protocol.

4.2.2 Exclusion Criteria:

None of these exclusion criteria should be met:

- Patient currently hospitalized or under immediate consideration for hospitalization;
- Patient currently in shock or with hemodynamic instability;
- Patient with severe hepatic disease (as *per* clinical judgement) or liver enzymes >2x the upper limit of normal;
- Female patient who is pregnant, breast-feeding, or is considering becoming pregnant during the study or for 1 day after the last dose of study medication;
- Patient currently taking Sirolimus, Tacrolimus, or other mTOR inhibitors for other indications (mainly chronic indications represented by organ transplantation or autoimmune diseases);

- On Warfarin therapy; Subjects taking any of the medications listed in Appendix C may participate if they are otherwise eligible AND the medication can be safely held during the following times:

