6.2 Dosage Regimen

At randomization, patients will be dispensed Fisetin capsules or placebo to match Fisetin capsules. Patients will be instructed to take 20mg/kg on days 0 and 1 and another 20mg/kg on days 8 and 9 according to the detailed set of dispensing instructions outlined on the label.

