Appendix A Detailed Study Safety Parameters

1. Demographics and Medical/Surgical History

The following elements of demographics, medical/surgical history will be recorded at the Screening Visit:

- age
- ethnic origin
- sex
- smoking history
- history of diabetes
- history of hypertension
- history of dyslipidemia
- prior cardiac events/heart failure
- prior obstructive pulmonary disease
- prior other respiratory disease

2. Physical Appearance

- 1. weight
- 2. height
- 3. BMI \geq 30 kg/m²

4. Detailed Visit Summary

Screening Visit (Days -2 to 0)

Patients will be pre-screened and inclusion and exclusion criteria will be reviewed prior to being recruited for the study.

- Screening Labs (within 6 months prior to randomization): CBC with diff and comprehensive metabolic panel with assessment of liver and kidney function tests
- Pregnancy test (women of childbearing potential)

Subjects who qualify should be immediately randomized. Randomization and dosing should occur on the same day if possible.

Baseline (Day 0 & Day 1) – IP Administration

- Mail in kit for buccal swab, urine and stool sample prior to first dose of IP administration, if applicable
- SF 36 Health Survey
- Determination of Ordinal Scale Score.
- The 1st IP administration will occur on Day 0.
- The 2nd IP administration will occur on Day 1 (12 -36 hours after the 1st IP administration).
- Day 8 & Day 9 IP Administration Phone call visit with the study team as a reminder for IP administration. This call can occur within a 2 day window (+ or -) of day 8; study drug administration will still occur on day 8 and day 9.
- Determination of Ordinal Scale score.
- Review of adverse events.
- SF-36 Health Survey

- The 3rd IP administration will occur on Day 8.
- The 4th IP administration will occur on Day 9 (12- 36 hours after the 3rd IP administration).

Day $15 - (\pm 2 \text{ days})$

- Determination of Ordinal Scale score.
- Review of adverse events.
- SF-36 Health Survey
- Mail in kit for buccal swab, urine and stool sample, if feasible

Day 30 (-2 to +7 days)

- Determination of Ordinal Scale score.
- Review of adverse events.
- SF-36 Health Survey
- Mail in kit for buccal swab, urine and stool sample, if feasible

Day 60 (±14 days)

- Determination of Ordinal Scale score.
- Review of adverse events.
- SF-36 Health Survey
- Mail in kit for buccal swab, urine and stool sample, if feasible

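### Five Appendix C rows are written for two doses, while the regimen has four and the appendix's own opening rule covers both dosing pairs

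*Combined protocol and SAP*

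**What the plan says.** **Regimen.** Section 6.2 states "Patients will be instructed to take 20mg/kg on days 0 and 1 and another 20mg/kg on days 8 and 9". The Synopsis counts this as four doses. Appendix A numbers them first to fourth, for example "The 4th IP administration will occur on Day 9 (12- 36 hours after the 3rd IP administration").

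**General rule.** Section 4.2.2 states "Subjects taking any of the medications listed in Appendix C may participate if they are otherwise eligible AND the medication can be safely held" in two windows. The first runs from before dose 1 until at least 10 hours after dose 2. The second is "Immediately before the 3rd IP administration (Day 8) until at least 10 hours after the 4th IP administration (Day 9"). The Synopsis exclusion criteria and the head of Appendix C say the same.

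**Drug-specific rows, in the sensitive-substrates table of Appendix C.**
- Colchicine: "Colchicine (½ dose QD until 10 hours after the last (2 nd) IP" administration.
- Atorvastatin: "Atorvastatin (QOD or ½ dose QD until 10 hours after the last", continuing "2 nd) IP administration; unless willing to modify as directed".
- Rosuvastatin: the same schedule and the same end-point.
- Desipramine: alternate-day dosing or a hold, with the same end-point.
- Venlafaxine: one dose omitted on day 2 of study drug, then normal dosing.

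None of these rows mentions a third or fourth dose, and no text says whether a row replaces the general hold.

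**The concern.** In a four-dose regimen the last dose is the fourth. A row that calls the second dose the last one either stops too early or uses a numbering that the protocol does not explain. The action differs as well: halving a drug, or giving it on alternate days, is not holding it. Staff therefore find two instructions for the same drug in one appendix, and the more specific one names the drug.

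The stake is drug-interaction safety around Days 8 and 9. Section 1.1 (Investigational Product) promises precaution because Fisetin inhibits CYP enzymes, and Section 1.5 makes its low-risk statement conditional on the medication criteria. Section 4.3, despite its title, gives no rule on prohibited drugs, so Appendix C and the exclusion criterion pointing to it are the working instruction. Diabetes and coronary disease are qualifying risk factors, so patients taking statins are foreseeable.

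The whole drug supply is handed out on Day 0 (Section 3.4), so the directions need to be right from the start. Under Section 5.2.1, a non-serious event reaches the eCRF only if it is gastrointestinal, attributed to study drug, or a clinically significant laboratory finding. Some interaction effects could therefore go unrecorded.

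**Working it through.** No power, alpha or sample-size figure is involved. The check sets the rows against the dosing schedule and counts.

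**Inputs**
- Dosing days 0, 1, 8 and 9, doses 1 to 4 (Synopsis; Section 6.2; Appendix A).
- Dose 2 falls 12 to 36 hours after dose 1 (Appendix A).
- Rows ending at the second dose: colchicine, atorvastatin, rosuvastatin, desipramine = 4. Venlafaxine, with its single skip, makes 5.

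**Step 1: when a row's modification ends, read literally.** It ends 10 hours after dose 2.
- Earliest: 12 + 10 = 22 hours after dose 1.
- Latest: 36 + 10 = 46 hours after dose 1.
- Dose 3 is on Day 8, so nothing in these rows reaches doses 3 and 4.

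**Step 2: coverage under each reading**

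| Reading | Four rows: doses with no precaution | Venlafaxine: dosing days with the drug skipped |
|---|---|---|
| Opening rule governs (full hold) | 0 of 4 | 4 of 4 |
| Row governs, read literally | 2 of 4 (doses 3 and 4) | 1 of 4 (Day 1) |
| Row governs, read per two-day course | 0 of 4 | 2 of 4 (Days 1 and 9) |

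For venlafaxine, day 2 of study drug is taken to be the second day on drug, which is Day 1 in the protocol's numbering.

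**Step 3: can a row and the opening rule both be followed?** Each window contains two consecutive dosing days. An alternate-day schedule puts a dose on one of them, and a half dose daily puts one on both. Neither is a hold. Desipramine's hold option is compatible with the rule in the first window, but on the literal reading it stops before the second.

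**Step 4: which meaning of the second dose does the text favour?**
- For the whole regimen: Appendix A and the head of Appendix C call the later doses the third and fourth. Section 1.1 (Investigational Product) still describes a single course that "will be administered orally for 2 consecutive days on study Days 0 and 1".
- For each course: the population description in Section 1.1 (Background) speaks of two days of treatment and then lists Days 0-1 and 8-9, as if one two-day course were given twice.
- No sentence settles it.

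**The case against.** The strongest reply is that Days 8 and 9 are already covered. The two-window hold appears three times, applies to any drug listed in Appendix C, names the third and fourth doses, and has no exception. The five rows sit inside that appendix. For a patient to be left without a precaution, a row would have to override the rule, and no text says that it does. This stands. A reader might infer that the plan leaves doses 3 and 4 unprotected for these drugs; the documents do not support that.

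The per-course reading is also reasonable, given the Background wording. It removes the gap in the four rows. It does not reconcile a reduced dose with a hold, and the explicit first-to-fourth numbering weighs against it.

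There is partial mitigation. Table 1 schedules a concomitant-medication review at the Day 8 call, which Appendix A describes as a dosing reminder. That call may come up to 2 days late, on Day 10, after dose 4 on Day 9.

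A reader might also extend the criticism to every entry that seems to allow something less than a hold. That goes too far. The repaglinide entry asks only for close glucose monitoring, which can accompany a hold, and the azole entry has nothing to do with the two-dose wording.

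**Conclusion.** The point holds as a conflict in operative safety instructions. Five rows are worded for a two-dose regimen, and the rule above them is worded for four. If a site follows the rows literally, 2 of 4 doses have no row-level precaution for colchicine, atorvastatin, rosuvastatin and desipramine, and venlafaxine is skipped on 1 of 4 dosing days. On the per-course reading the figures are 0 of 4 and 2 of 4. If the opening rule governs, all four doses are covered by a full hold.

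The adverse figures assume that staff follow the row and not the rule. The wording makes this plausible, because a half-dose instruction has no purpose if the drug must be held anyway, but the documents do not direct it. That the rows were carried over from a two-dose regimen would fit the text, but it is an inference. The number of patients affected cannot be derived. Power, type I error and the planned analyses are unaffected. The rows should be corrected because the wording is wrong as it stands and the correction is simple.

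**What to change.** 1. Restate the colchicine, atorvastatin, rosuvastatin and desipramine rows so that each modification runs from before dose 1 (Day 0) to 10 hours after dose 2 (Day 1), and again from before dose 3 (Day 8) to 10 hours after dose 4 (Day 9).
2. State the venlafaxine skip in study-day numbering: Day 1 and Day 9.
3. Add one sentence at the head of Appendix C saying that, where a row gives a drug-specific modification, it applies in place of the full hold in both windows. If the sponsor's clinicians require the full hold, delete the row modifications instead, and steps 1 and 2 fall away.

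The choice in step 3 is clinical. The cost is a wording change to Appendix C, with a matching cross-reference in the exclusion criterion if the modifications are kept. Design, sample size and analysis do not change.
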